Potential risk of clinical significance	Summary of data/rationale for risk	Mitigation strategy
Dyspnea	
In in vitro studies, AZD0780 is an adenosine transport inhibitor (IC50 ~15 <math>\mu</math>M). Inhibition of adenosine transporters can result in dyspnea and bronchospasm in patients with respiratory disease. In addition, inhibition of <math>\alpha</math>1A adrenoceptors (Ki=18 <math>\mu</math>M and functional IC50 ~47 <math>\mu</math>M) identified in AZD0780 in vitro studies, can result in dyspnea, observed in clinical trials with <math>\alpha</math>-adrenoceptor antagonists.
 
The respiratory safety pharmacology study with AZD0780 in rats did not show any effect on respiratory parameters as assessed by plethysmography.
	
 
Exclusion of participants with any uncontrolled or serious disease, or any medical (eg, known major active infection or major hematological, renal, metabolic, gastrointestinal, respiratory, or endocrine dysfunction) or surgical condition that, in the opinion of the investigator, may either interfere with participation in the clinical study and/or put the participant at significant risk (exclusion criterion 3).
 
Adverse events, physical examinations and vital signs, including respiratory rate and pulse oximetry, will be monitored throughout the study.
 
Individual stopping criteria have been defined to consider exacerbation of respiratory disease.
 

Effects on Reproduction	
AZD0780 was shown to be an antagonist of the serotonin receptor 5-hydroxytryptamine receptor 2B (5-HT2B). Possible adverse effects of 5-HT2B receptor antagonism include developmental toxicity (based on complete knockout).
 
AZD0780 inhibits <math>\alpha</math>1A adrenoceptor. In clinical studies <math>\alpha</math>1A adrenoceptor antagonism has resulted in a reduction of uterine and vas deferens contractility and AE reports of abnormal ejaculation.
 
Nonclinical developmental toxicity studies for AZD0780 have not yet been performed.
	
 
Women of childbearing potential will be excluded from the study (inclusion criteria 1 and 8).
 
Reproductive restrictions will be in place throughout the study.
 

Potential risk of clinical significance	Summary of data/rationale for risk	Mitigation strategy

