4.6.5 Vital Signs

4.6.5.1 Definitions and Derivations

The following vital signs will be measured:

- Body weight (kg)
- Body temperature (degrees Celsius)
- Heart (pulse) rate (bpm)
- Respiratory rate (1/min)
- Oxygen saturation (SpO₂)
- Systolic blood pressure (SBP) (mmHg)
- Diastolic blood pressure (DBP) (mmHg)

Vital signs will be collected at the visits indicated in the SoA (see CSP).

Additionally, vital signs values will be classified as normal (if value is within normal reference range), low (if value is below the normal reference range or limit), and high (if value is above the normal reference range or limit) according to the normal reference values given in [Table 11](#) below. Based on the categories presented in [Table 11](#) variables may have 2-level classification and 3-level classification.

Systolic and diastolic blood pressure will be measured in triplicates and the mean of the three measurements will be collected in the EDC and used in the subsequent analyses.

Table 11 - Vital Signs Normal Reference Ranges

Parameter	Normal reference range
Systolic blood pressure	< 140 mmHg
Diastolic blood pressure	< 90 mmHg
Heart (pulse) rate	50-100 bpm
Body temperature	≤ 37°C
Oxygen saturation	≥ 95%
Respiratory rate	12-20 per minute

Abnormalities in Vital Signs

Treatment emergent abnormalities are defined as abnormalities that manifested after the first administration of study treatment.

The presence of the abnormalities will be determined based on the following criteria (at any time during treatment/study, as applicable):

1. Systolic blood pressure
 - a. Maximum value is > 40 mmHg increase from baseline
 - b. Maximum value is > 180 mmHg
 - c. Maximum value is ≥ 140 mmHg with ≥ 20 mmHg increase from baseline
 - d. Maximum value is ≥ 160 mmHg with ≥ 30 mmHg increase from baseline
 - e. Maximum value is ≥ 180 mmHg with ≥ 40 mmHg increase from baseline
 - f. For change from baseline to mean value
 - i. > 10 mmHg
 - ii. > 20 mmHg
 - iii. > 30 mmHg
 - iv. > 40 mmHg
2. Diastolic blood pressure
 - a. Maximum value is > 20 mmHg increase from baseline
 - b. Maximum value is > 100 mmHg
 - c. Maximum value is ≥ 90 mmHg with ≥ 10 mmHg increase from baseline
 - d. Maximum value is ≥ 100 mmHg with ≥ 20 mmHg increase from baseline
 - e. For change from baseline to mean value
 - i. > 10 mmHg
 - ii. > 20 mmHg
 - iii. > 30 mmHg
 - iv. > 40 mmHg
3. Heart rate

- a. Maximum value is > 100 beats/min with > 20 beats/min increase from baseline

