4.6.5.2 Presentations

Observed values and change from baseline in vital signs will be summarised by the treatment group and visit with descriptive statistics.

A figure with mean change from baseline over time by treatment group will be presented.

Shift tables from baseline to maximum on-treatment and on-study value (excluding Oxygen Saturation, because shift to maximum is not relevant), from baseline to minimum on-treatment and on-study value will be presented for each treatment group and AZD0780 Total.

Treatment emergent vital signs abnormalities will be reported as defined in Section 4.6.5.1.

Risk differences between active treatment groups and Placebo will be presented, alongside 95% confidence intervals of the risk difference according to the definitions in Section 4.6.3.1.

The key subject information about the treatment emergent vital signs abnormalities will also be listed. Additionally, individual vital signs data will be listed.

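### Oxygen saturation and respiratory rate, named as monitoring for the dyspnea risk, have no treatment-emergent criterion in the SAP and so no risk difference against placebo

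*SAP*

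**What the plan says.** **Protocol.** In the dyspnea row of Table 2, the rationale is that "Inhibition of adenosine transporters can result in dyspnea and bronchospasm in patients with respiratory disease". The mitigation has three parts: exclusion criterion 3, monitoring, and a stopping rule. The monitoring sentence reads "Adverse events, physical examinations and vital signs, including respiratory rate and pulse oximetry, will be monitored throughout the study", and the stopping-rule sentence reads "Individual stopping criteria have been defined to consider exacerbation of respiratory disease". Section 7.1.3 gives that rule as an exacerbation of known respiratory disease needing hospital admission.

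**SAP.** Section 4.6.5.1 lists SpO2 and respiratory rate among the measured vital signs, and Table 11 gives each a reference range. For treatment-emergent abnormalities it then says "The presence of the abnormalities will be determined based on the following criteria (at any time during treatment/study, as applicable", followed by three numbered entries: systolic pressure, diastolic pressure and heart rate. Section 4.6.5.2 ties the abnormality report to that list ("Treatment emergent vital signs abnormalities will be reported as defined in Section 4.6.5.1"), and the risk differences with 95% confidence intervals and the key-subject listing accompany that report. The same section also plans by-visit summaries of observed value and change, shift tables, and listings of individual data.

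**The concern.** The two vital signs that Table 2 singles out for a named potential risk are left out of the only vital-signs output that compares counts with placebo. Heart rate, which has no row of its own in Table 2, is included. The SAP's general sentence, that abnormalities arising after first dose are treatment-emergent, does not fill the gap, because the next sentence makes the list decide whether an abnormality is present.

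At stake is how well the study can describe one safety question. A small excess of participants on active treatment with falling saturation or rising respiratory rate would not appear as a count with an interval. If those participants began outside the reference range, the shift table would not show their worsening either.

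**Working it through.** No sample-size, power or alpha figure is involved, so there is no planned number to reproduce. The check is a reading of the outputs, then a short illustration.

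**1. Criteria per parameter (SAP 4.6.5.1, counting sub-items).** Systolic pressure 9, diastolic pressure 8, heart rate 3, SpO2 0, respiratory rate 0.

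**2. The SAP's shift categories applied to example values.** SpO2 has two levels, Low (<95%) and Normal (≥95%), and is tabulated from baseline to minimum. Respiratory rate has Low (<12), Normal (12–20) and High (>20).

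| Measure | Baseline to worst | Cell |
|---|---|---|
| SpO2 | 95 to 94 | Normal to Low |
| SpO2 | 97 to 88 | Normal to Low |
| SpO2 | 94 to 94 | Low to Low |
| SpO2 | 94 to 85 | Low to Low |
| Respiratory rate | 18 to 22 | Normal to High |
| Respiratory rate | 22 to 22 | High to High |
| Respiratory rate | 22 to 32 | High to High |

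A new departure from the normal range is counted. Worsening from outside it shares a cell with no change. Depth is also lost for normal starters: 95 to 94 and 97 to 88 share a cell.

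**3. Where such worsening still appears.**
- By-visit change from baseline (4.6.5.2), with minimum and maximum under the default statistics of SAP 3.3.1.
- Individual vital-signs listings.
- Adverse event tables, if the change is serious, is the reason for stopping study drug, or is judged clinically relevant (Protocol 8.3.4).

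**4. Can such participants enroll?** No eligibility criterion sets a limit on SpO2 or respiratory rate. Exclusion 3 rests on the investigator's opinion, and Section 7.1.3 presupposes participants with known respiratory disease. The share starting outside the range is not given. If it is a fraction f of an arm of about 75 (Protocol 6.3), the count is 75 × f: 0 at f = 0, 2.25 at 3%, 7.5 at 10%. These fractions are assumptions.

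**5. Illustration of what a count adds.** Assume 75 per arm, a 6-point SpO2 fall in k active participants, and no placebo participant meeting a change criterion. The mean moves by −6k/75. The risk difference uses the formula in SAP 4.6.3.1 with p = k/75, taking the variance as p(1−p)/75: p ± 1.96 × √(p(1−p)/75).

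| k | Mean change (points) | Risk difference, % (95% CI) |
|---|---|---|
| 2 | −0.16 | 2.7 (−1.0 to 6.3) |
| 3 | −0.24 | 4.0 (−0.4 to 8.4) |
| 5 | −0.40 | 6.7 (1.0 to 12.3) |
| 8 | −0.64 | 10.7 (3.7 to 17.7) |

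Placebo noise events would widen these intervals. The table contrasts two summaries of the same data and predicts nothing.

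**The case against.** A reader might infer that such falls are counted nowhere. The documents do not support that. The participant is in the Low-to-Low cell, the fall enters the change summaries and listings, and a clinically relevant fall becomes an adverse event tabulated by arm. A 6-point fall also forces that arm's minimum change at that visit to −6 or lower. What remains is that a minimum shows one extreme, not how many participants fell, and that listings make no comparison with placebo.

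A reader might also infer that the protocol depends on these two measures for dyspnea. It does not: adverse events, physical examination, exclusion 3 and the stopping rule stand beside them. Dyspnea is a symptom, so adverse event reporting is its most direct measure. That stands and lowers the importance of the gap.

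The contrast with blood pressure has some basis. The first two criteria for each pressure match the stopping thresholds in Protocol 7.1.2, while the respiratory rule has no SpO2 or rate threshold to mirror. Table 2 also reports a pressure rise in monkeys but no respiratory effect in rats. This explains only part of the difference. The heart-rate criteria use 100, 50 and 60 beats/min, whereas the stopping thresholds are 125, 40 and 30.

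Yield is limited too. Vital signs are taken before dosing at visits (Protocol 8.2.2), so extra rows describe pre-dose values, and symptoms between visits reach the data through the adverse event question. That stands.

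**Conclusion.** The point holds in a limited form. SpO2 and respiratory rate have no treatment-emergent criterion, hence no treatment-emergent count, risk difference or key-subject listing. Worsening from an already abnormal baseline is not distinguished in the shift tables. For participants who start within range, a fall below 95% or a rise above 20/min is counted by arm, though without a risk difference or interval.

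The size cannot be stated, because baseline distributions are not given; the number affected could be near zero. A reader might equate baseline SpO2 below 95% with the respiratory-disease group in Table 2. No section makes that link, and participants with controlled disease may start at or above 95%.

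The primary analysis is untouched. This is a useful, low-priority improvement to safety reporting.

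**What to change.** Before unblinding, add to SAP 4.6.5.1 at least one treatment-emergent criterion for SpO2 based on a decrease from baseline, and at least one for respiratory rate based on an increase. Carry both into the 4.6.5.2 abnormality table, risk differences and key-subject listing. A criterion that only repeats crossing the reference limit would largely duplicate existing shift cells; the change-based one is what adds information.

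The sponsor's clinical team should set the cut-offs while blinded. If the optional interim analysis takes place, members of the Unblinded Review Committee should not take part in setting them. The cut-offs are analysis thresholds only and alter no stopping or treatment rule.

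The cost is SAP wording and a few rows in planned tables, from data already collected at every visit. The downside is some events from measurement noise in every arm, against which the placebo arm gives a reference.

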4.6.6 Electrocardiogram

4.6.6.1 Definitions and Derivations

At visits specified in the Schedule of activities (CSP), 12-lead ECG will be obtained in triplicates, using the study site's own ECG machines. The following variables will be collected: PR interval, RR interval, QRS duration, QT and QTcF intervals, and heart rate. All ECG parameters will be measured in triplicates and the mean value will be entered to the EDC system and will be used in subsequent calculations. Additionally, an overall evaluation of ECG results will also be performed.

Abnormalities in ECG

Treatment emergent abnormalities in QTcF at any visit will be summarised using following criteria:

- QTcF value above specific ms at any time:
 - > 450 and \leq 480 (ms)
 - > 480 and \leq 500 (ms)
 - > 500 (ms)

- QTcF increase from baseline by more than specific ms at any time:
 - > 30 and \leq 60 (ms)
 - > 60 (ms)
- QTcF value above specific ms and QTcF increase from baseline by more than specific ms at any time:
 - Value > 450 and \leq 500 (ms) and increase > 30 and \leq 60 (ms)
 - Value > 500 (ms) and increase > 60 (ms)
 - Value > 450 and \leq 500 (ms) and increase > 60 (ms)
 - Value > 500 (ms) and increase > 30 and \leq 60 (ms)

Shift Tables

Shift tables will be presented for ECG parameters according to the following categories: "normal", "borderline", "abnormal, not clinically significant", and "abnormal, clinically significant".

4.6.6.2 Presentations

Descriptive statistics per visit and change from baseline will be presented for all parameters.

Treatment emergent electrocardiogram abnormalities by predefined criteria (Section [4.6.6.1](#)) will be presented.

ECG overall assessment (report by "normal", "borderline", "abnormal, not clinically significant", and "abnormal, clinically significant") at baseline versus the last value on-treatment and on-study will be presented. Shift table from baseline to worst on-treatment and on-study value will also be presented. Key subject information about treatment emergent ECG abnormalities will be listed. Additionally, measurements of individual ECG data and abnormalities in ECG will be presented in the listings.

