**Table 2 Risk Assessment of AZD0780**

Potential risk of clinical significance	Summary of data/rationale for risk	Mitigation strategy
QT-prolongation	
In an in vitro assay, AZD0780 was shown to be an inhibitor of the hERG channel (human ether-a-go-go-related gene). hERG channel inhibition can cause QT-prolongation and potentially cardiac arrhythmia, including Torsade de Pointes. Based on the in vitro data, modeling predicted a high likelihood of QT-prolongation at free plasma levels of AZD0780 at doses to be investigated in AZD0780 clinical studies.
 
In the cardiovascular safety studies and the 1 month toxicology study of AZD0780 in cynomolgus monkeys, although QT-prolongation was observed, the pre-clinical data were consistent with a reversible mode of hERG channel inhibition and QT-prolongation. There were no observations of AZD0780 related arrhythmias in the in vivo studies at the dose levels tested.
 
No ECG findings of safety concern have been identified in the ongoing phase 1 clinical study (Study D7960C00001) at single doses of up to [REDACTED] mg or repeated doses up to [REDACTED] mg once daily.
	
 
Exclusion of participants with clinically important abnormalities in rhythm, conduction or morphology of the resting ECG and any clinically important abnormalities in the 12 lead ECG; QTcF > 450 ms; AV-block grade II-III; sinus node dysfunction with significant sinus pause untreated with pacemaker; and cardiac tachyarrhythmias (exclusion criteria 13-14).
 
Regular ECG recordings and assessment.
 
Individual stopping criteria have been defined to consider QTc and QTcF values outside pre-specified ranges.
 

Blood pressure elevation	
In the cardiovascular safety studies of AZD0780 in cynomolgus monkeys, a transient increase in arterial BP was observed between 0.5h – 8h post dose at the highest tested dose of [REDACTED] mg/kg (free Cmax of [REDACTED] µmol/L).
	
 
Only participants within a defined range of BP will be included in the study (exclusion criterion 10).
 
It is recommended that antihypertensive treatment is considered/initiated at the PI's discretion and in accordance with applicable clinical guidelines in order to optimize blood pressure for participants with hypertension during the clinical study. BP will be monitored throughout the study.
 

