#### 4.2.3 Rationale for Selection of Comparator

The comparator in this study is placebo. Both AZD0780 and placebo will be administered on top of moderate or high-intensity statin therapy; therefore, the treatment of the placebo group will correspond to current SoC for participants with dyslipidemia.

The use of placebo will allow for a double-blinded treatment period and to provide a control arm, so as to enable a continued comparison of efficacy, in particular the comparison of dose-dependent change in LDL-C after oral administration of multiple doses of AZD0780, and to act as a comparator to contextualize safety observations.

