#### **9.4.3 Safety**

Safety data will be summarized descriptively and will not be formally tested.

Safety data will be presented in the data listings.

Adverse events will be summarized by PT and SOC using MedDRA vocabulary.

Furthermore, listings of SAEs and AEs that led to withdrawal will be made and the number of participants who had any AE, SAEs, AEs that led to withdrawal, and AEs with severe intensity will be summarized.

Tabulations and listings of data for vital signs, clinical laboratory tests be presented. Results from safety ECGs will only be listed. Any new or aggravated clinically relevant abnormal

medical physical examination finding compared to the baseline assessment will be reported as an AE.

Out-of-range values for safety laboratory will be flagged in individual listings as well as summarized descriptively.

Safety analyses will be performed using the safety analysis set unless otherwise specified. Details of safety analyses will be provided in the SAP.

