2 CHANGES TO PROTOCOL PLANNED ANALYSES

- ECG parameters will be presented descriptively, treatment emergent abnormalities will be summarized, shift tables will be produced and key subject information will be listed.
- Multiplicity adjustments will not be applied for any of the secondary endpoints, and will have nominal p-values presented only.
- Two subcategories of the intercurrent event ‘change in background therapy’ are introduced:
 - ‘Change in background lipid lowering statin therapy’
 - ‘Initiation, change or discontinuation in non-prohibited background lipid lowering non-statin therapy’ to account for non-statin therapies (such as ezetimibe and bempedoic acid) when assessing the treatment effects.
- The ICE ‘Prohibited medication intake’ is clarified as ‘intake of prohibited medication affecting lipid parameters’.
- Addition of the ICE ‘Prohibited medication not affecting lipid parameters’, ‘intake of any other concomitant medication’, and ‘death’.

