4.6.3.2 Presentations

All laboratory data will be presented for the on-treatment and on-study periods using international system of units and presented as detailed in [Table 2](#).

Clinical laboratory parameters will be presented by scheduled visit, separately for haematology and chemistry parameters. All parameters will be presented as continuous variables with descriptive statistics for all visits at which an assessment is scheduled. Observed value, absolute change from baseline will be presented using descriptive statistics for all scheduled assessments after baseline.

The number of participants with treatment-emergent laboratory parameter abnormalities will be presented categorically in frequency tables, according to the categories defined in Section [4.6.3.1](#). Risk differences between active treatment groups and Placebo will be presented with 95% CI.

Key subject information will be separately listed for participants with haematology abnormalities, chemistry abnormalities, or potential Hy's law. Additionally, individual chemistry laboratory measurements and individual haematology laboratory measurements will be listed.

Shift tables from baseline to maximum on-treatment and on-study value, and from baseline to minimum on-treatment and on-study value will be presented by treatment group according to the categories defined in Section [4.6.3.1](#).

A descriptive table for maximum ALT and AST versus maximum total bilirubin for the on-treatment and on-study analysis periods will be shown.

Out-of-range values for safety laboratory will be flagged in individual listings as well as summarized descriptively.

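### ECG is the only safety-test domain with no pre-specified comparison against placebo, although QT prolongation is a named risk of the drug

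*SAP*

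**What the plan says.** **ECG.** Protocol 9.4.3 says "Results from safety ECGs will only be listed". SAP Section 2 records a deliberate extension: "ECG parameters will be presented descriptively, treatment emergent abnormalities will be summarized, shift tables will be produced and key subject information will be listed". SAP 4.6.6.1 then states "Treatment emergent abnormalities in QTcF at any visit will be summarised using following criteria" and gives bands of absolute QTcF, of increase from baseline, and of the two combined. SAP 4.6.6.2 adds that "Descriptive statistics per visit and change from baseline will be presented for all parameters", with shift tables of the overall reading and listings. Neither section mentions a difference from placebo or an interval.

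**The other test domains.** For blood laboratory abnormalities, SAP 4.6.3.2 says "Risk differences between active treatment groups and Placebo will be presented with 95% CI". For vital signs, SAP 4.6.5.2 says "Risk differences between active treatment groups and Placebo will be presented, alongside 95% confidence intervals of the risk difference", and SAP 4.6.4.2 makes the same commitment for urinalysis. All three use the formula in SAP 4.6.3.1, a Wald interval on the difference of two proportions.

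**Why QT is of interest.** Protocol Table 2 lists QT prolongation as a potential risk and reports that "modeling predicted a high likelihood of QT-prolongation at free plasma levels of AZD0780 at doses to be investigated in AZD0780 clinical studies". The same row says that Phase I had so far raised no ECG concern. Protocol 4.2.3 gives one purpose of the placebo arm as "to act as a comparator to contextualize safety observations".

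**Optional modelling.** SAP 4.4 allows exposure-response modelling of safety but does not commit to it, leaves it to a separate plan and does not name QTcF.

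**The concern.** The plan names QT prolongation as a risk at the doses under study. It collects triplicate ECGs at every visit and keeps a placebo arm partly to put safety findings in context. Yet the domain in which that risk would appear is the one test domain with no planned contrast against placebo.

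If nothing is added, any statement about the size of the QTcF effect at a dose, or how large an effect the data make unlikely, will rest on a calculation chosen after the results are known. The protocol intends these data to guide later dose choice and safety monitoring, and an Unblinded Review Committee may weigh benefit and risk for Phase 3. An agreed estimate with its uncertainty would serve both better than arm-by-arm tables read by eye.

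**Working it through.** **1. What each test domain gets (from the SAP)**

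| Domain | SAP section | By-arm summary | Difference from placebo with 95% CI |
|---|---|---|---|
| Blood laboratory | 4.6.3.2 | yes | yes, proportions with an abnormality |
| Urinalysis | 4.6.4.2 | yes | yes, proportions |
| Vital signs | 4.6.5.2 | yes | yes, proportions |
| ECG | 4.6.6.2 | yes | none |

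Adverse events (SAP 4.6.2.2) also have no risk difference, so the statement is limited to the four test domains.

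**2. What can be derived from the planned tables.** SAP 3.3.1 defines the continuous summary as including n, mean and SD, and SAP Table 2 shows each dose and placebo for safety. A crude difference and interval at each dose and visit therefore follow by arithmetic. An interval for the visit average needs the within-person correlation between visits, which the tables do not show. A baseline-adjusted repeated-measures estimate needs participant-level data.

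**3. Numbers per arm.** Protocol 6.3 gives about 75 randomized per arm. Protocol 9.2 assumes 15% discontinuation: 375 × 0.85 = 318.75, and 318.75 / 5 = 63.75. This reproduces the stated figures of about 320 evaluable and 64 per arm. The protocol states no precision for QTcF.

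**4. Precision at one visit.** Unadjusted 95% half-width = 1.96 × SD × √(2/n). The SD of QTcF change is an assumption.

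| Assumed SD (ms) | n = 64 per arm | n = 75 per arm |
|---|---|---|
| 8 | 2.8 | 2.6 |
| 10 | 3.5 | 3.2 |
| 15 | 5.2 | 4.8 |
| 20 | 6.9 | 6.4 |

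Averaging five visits (Weeks 1, 2, 4, 8 and 12) with an assumed correlation of 0.5 multiplies these by √((1 + 4 × 0.5)/5) = 0.775. The range becomes about 2.0 to 5.4 ms. Baseline adjustment would be expected to narrow it further.

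**5. Bands against means (illustration only).** A simulation of 3,000 trials assumed 70 per arm, five visits, correlation 0.5, SD 12 or 15 ms and a true shift of 8 ms. The interval for the risk difference in any increase above 30 ms excluded zero in 63% to 64% of trials. The interval for the mean difference did so in 98% (SD 12) and 88% (SD 15) at Week 12 alone, and in at least 98% when averaged over visits. Increases above 60 ms occurred in about 0.1% of participants or fewer. The 8 ms is one chosen value, and the simulation assumes the full shift is present when the ECG is taken.

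**6. The Wald formula with sparse categories.** With n = 75 per arm:
- 3 v 0 events: 4.0% (−0.4% to 8.4%).
- 5 v 1 events: 5.3% (−0.9% to 11.6%).
- 0 v 0 events: 0% (0% to 0%), an interval of zero width.

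The exact two-sided 95% upper limit for 0/75 in one arm is 1 − 0.025^(1/75) = 4.8%. A Newcombe interval at 0 v 0 uses the Wilson limit 1.96²/(75 + 1.96²) = 3.84/78.84 = 4.9%, and so runs from −4.9% to 4.9%.

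**7. Timing.** In the Schedule of Activities, dosing runs from Day 1 to Day 84 and the Week 12 visit is Day 85, after the last scheduled dose. That visit still falls in the SAP's on-treatment period, which extends 10 days past the last dose. At the visits after Day 1 through Week 12, pharmacokinetic blood is drawn before the dose and participants hold their tablet until they are in the clinic (Protocol 8.4.1). Neither the schedule nor Protocol 8.2.3 fixes the ECG time relative to dose.

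**The case against.** A reader might infer that the trial will be unable to say, at any dose, what QT effect it showed or excluded. The documents do not support that. Arm-level n, mean and SD of QTcF change, placebo included, will be reported at every visit, so a crude difference can always be computed. Category risk differences can likewise be computed from the planned counts. What is missing is a pre-specified contrast and the adjusted or averaged version of it.

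Four further points stand in part:

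- **Consistency goes only so far.** The other three domains have risk differences in proportions. None has a modelled mean change. The argument from consistency supports the category comparison. The mean-change model rests on its own merit, namely that it is more sensitive to a modest shift.
- **The prior evidence is mixed.** The QT prediction comes from in vitro data and modelling, and Phase I had raised no ECG concern. Protocol Table 2 does not say that its row order is a ranking, so QT is a named risk, not an established or leading one.
- **A narrow interval could mislead.** Given the timing in the working, and ECGs recorded on each site's own equipment, the estimate may reflect QTcF near trough. It would not by itself exclude an effect near peak exposure.
- **Safety is not formally tested.** That is so, but an interval is not a test, and the SAP already gives intervals in three domains.

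The optional exposure-response work and the committee's charter may cover some of this. The first is not a commitment and the second is not available here.

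**Conclusion.** The gap is real but limited. ECG is the only one of the four safety-test domains with no pre-specified comparison against placebo. No baseline-adjusted or visit-averaged placebo-corrected QTcF effect with an interval is planned at any dose, so any such statement would be post hoc. The data can support it: about 2.6 to 6.9 ms half-width at one visit, unadjusted, for 64 to 75 per arm and an assumed SD of 8 to 20 ms. The averaged figure rests also on an assumed correlation of 0.5, and the simulated percentages on an assumed 8 ms shift; none of these is in the documents.

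This is a cheap and worthwhile improvement to the SAP, not a flaw that undermines the trial. It does not turn the study into one that can rule out QT prolongation.

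**What to change.** In SAP 4.6.6.2, on the safety analysis set and the on-treatment period, add as descriptive output without formal testing:

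1. The least squares mean difference in QTcF change from baseline, each dose minus placebo, by visit and averaged over Weeks 1 to 12, with 95% intervals. Use a repeated-measures model with baseline QTcF, treatment, visit and treatment-by-visit interaction.
2. Risk differences against placebo for the QTcF categories of SAP 4.6.6.1, with an interval valid at zero events (for example Miettinen-Nurminen or Newcombe) in place of the Wald formula of SAP 4.6.3.1.
3. A statement with the results that ECG time relative to dose is not specified and that the Week 12 ECG follows the last scheduled dose, so the estimate may describe QTcF near trough and does not by itself exclude an effect near peak exposure.

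The cost is SAP wording and two tables from data already collected. No visit, procedure or stopping rule changes. The downside is more descriptive intervals to interpret.
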